5.2 Endpoints

(ICH E9; 2.2.2)

Primary endpoint:

Proportion of subjects that remain on methotrexate with no intolerance one year after starting methotrexate. Intolerance is defined as ≥ 6 points in the English or French versions of the validated Methotrexate Intolerance Severity Score, MISS [1, 2]. The MISS questionnaire can be found in the appendix.

Secondary endpoints:

- 1) frequency and cumulative incidence of adverse events and any serious unexpected suspected adverse drug reactions (SUSARs).
- 2) the cumulative incidence of methotrexate intolerance within one year;
- 3) the cumulative incidence of attainment of inactive disease within one year defined by Wallace criteria [3] as modified by Guzman et al [4];
- 4) the cumulative incidence of starting a biologic medication within one year; and
- 5) the mean quality of life scores in the Quality of My Life scale 4-8 months after starting methotrexate [5];
- 6) the mean scores in the MISS questionnaire 4-8 months after starting methotrexate.

To enable future cost-effectiveness analysis, the EuroQol Collaboration 5-dimension scale for quality of life for youth parent-proxy questionnaire (EQ-5D-Y) is completed at every visit, for calculation of quality-adjusted life years [6], and medication costs will be calculated using the prices from the Ontario Drug Benefit Formulary [7].

Assessment of outcomes are completed at all clinic visits scheduled as per medical need using the CAPRI Registry (usual practice is every 1-4 months). OPT-JIA does not include additional trial-specific visits.

6 Study Methods

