6.3 Randomization and Blinding

(ICH E3; 9.4.3, 9.4.6. ICH E9; 2.3.1, 2.3.2)

Patients are assigned 1:1 online after confirming eligibility, using the Registry and block randomization by Canadian region and patient weight to one of two groups:

Intervention	routine premedication with oral ondansetron (2 mg if <15Kg, 4 mg if 15-30Kg, 8 mg if >30Kg; 3 doses a week)
Control	oral ondansetron at the same dosing, prescribed only to those who develop methotrexate-induced nausea/vomiting during usual care.

There is no blinding (masking) of treatment assignment.

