6.4 Study Assessments

(ICH E3; 9.5.1. ICH E9; 2.2.2)

Visit	Baseline	Every Visit	Visit Month 12
History and examination	x	x	x
QOL questionnaire	x	x (\pm 14)	x (\pm 14)
MISS	x	x (\pm 14)	x (\pm 14)
Actionable AEs	x	x	x
SAEs	x	x	x
SUSARs	x	x	x
Concomitant medication	x	x	x
Methotrexate use and dose	x	x	x
Ondansetron use and dose	x	x	x

Analysis Time Windows

Visit (target day)	Lower bound (days)	Upper bound (days)
Baseline (0)	N/A	N/A
Every visit to clinic (time window not applicable)	N/A	N/A
Month 4-8 (180)	120	240
Month 12 (364)	308	420

7 Sample Size

(ICH E3; 9.7.2. ICH E9; 3.5)

Our primary outcome statistic is the ratio of two proportions (relative risk, RR): the proportion of randomized children remaining on methotrexate with no intolerance in the intervention group divided by the same in the control group. Our sample size calculation is based on expressing the RR in the log scale and using established formulas for standard errors [15, 16]. With $p<0.05$, power of 90% and expected methotrexate continuation with no intolerance of 50% in the control group and 75% in the intervention group the result is 79 evaluable subjects per group. We will aim to recruit 176 subjects total to allow for up to a 10% dropout rate.

8 General Analysis Considerations

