8.5.3 Scope of Adaptations

The trial steering committee, with approval from the DSC, elected to conduct the interim analysis at an earlier stage of the trial than initially planned. Because of challenges relating to the COVID19 pandemic and other reasons, recruitment into the study had been much slower than anticipated, and there were concerns that the initial planned sample size might be unattainable within a reasonable time frame. The interim analysis was rescheduled to take place using all available enrolments into the study as of September 30, 2023.

Because the analysis would be based on a much smaller fraction of the intended sample size, the OPT-JIA PI and the study statistician proposed, and the DSC agreed, to base the analysis on the confidence interval for relative risk computed using the ratio of two estimates of the probability of successful trial completion from independently estimated Kaplan Meier curves. These estimates would better account for the partial information available from patients who did not have sufficient time in the study to complete the 52-week observation period.

To make use of all available information from patients who had not completed the trial yet, the definition of the primary end point was modified as follows. Visit times were shown in weeks since enrolment in OPT-JIA. We used 52 weeks to represent the 1-year visit as required for determining success. Failure was determined to have occurred if any of the criteria for failure -- stopping methotrexate or experiencing intolerance -- were observed during any visit up to and including 52 weeks. Success was determined to have occurred if no failure criteria were met at or before 52 weeks, and the patient had at least one visit at or after 52 weeks. All other patients were considered censored as of the time of their last visit; i.e., they were known not to have failed yet, but they had not yet provided a visit at or beyond 52 weeks to declare success.

The second adaptation was the use of the O'Brien-Fleming adjustment to type 1 error rate for the calculation of the confidence interval in the interim analysis [17]. This adjustment resulted in calculation of a 99.55% confidence interval for the interim analysis instead of the 95% mentioned in the protocol. The rationale being that both the interim and the final analysis together would then have a 5% chance of a positive result if the intervention is no more effective than control.

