10.1 Primary Efficacy Analysis

The primary efficacy analysis is an intention to treat analysis comparing all subjects randomized to intervention to all subjects randomized to control. The primary efficacy analysis will include one primary endpoint and five secondary endpoints as described below.

Proportion of children who remain on methotrexate with no intolerance one year after starting methotrexate (Primary Endpoint): The primary endpoint (remain on methotrexate with no intolerance one year after starting methotrexate) has two components ("remain on methotrexate" and "no intolerance"). At every visit to the clinic the physician reports whether the patient is receiving methotrexate (MTX = 1) or not (MTX = 0). Temporarily not taking (holding) methotrexate due to intercurrent illnesses, running out of the medication, or similar reasons will not be considered a failure. If the reason for not taking methotrexate at one visit is unclear after review of the full record by the principal investigator, records will be verified with the site investigator. No intolerance means no MISS score of 6 or more points was ever recorded for that patient during the 52-week trial. Since the actual date the first methotrexate dose is given at home varies from family to family and it is not reliably recorded, we use the date of enrolment in OPT-JIA to calculate the 52 weeks of trial duration. Since OPT-JIA is a pragmatic trial and does not have study-specific visits, the visit

closest to 52 weeks is used, with a broad window of observation of 8 weeks before and 8 weeks after 52 weeks. To clearly differentiate between patients who dropped out and those who simply didn't have a visit on time, all available registry visits for all OPT-JIA participants will be provided to conduct the final analysis. Patients will be counted as successes rather than as censored if they have further registry visits beyond 52 weeks and had no failed before 52 weeks.

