Our primary outcome statistic is the ratio of two proportions (relative risk, RR): the proportion of randomized children remaining on methotrexate with no intolerance one year after enrolment in the intervention group divided by the same in the control group. Subjects stopping ondansetron or methotrexate for toxicity or lack of efficacy will be counted as trial failures in calculations for the primary endpoint, irrespective of their MISS scores. A 95% CI for the RR will be calculated and the null hypothesis will be rejected if the confidence interval is entirely above 1. Considering that an interim analysis will be conducted, the alpha used in the final analysis will be 0.05 minus the alpha used in the interim analysis. As stated above, due to patient withdrawals and the fact that OPT-JIA did not have fixed-date visits, a number of patients was expected not to have a documented primary endpoint within the 52-week window, and a decision was made to use instead the Kaplan Meier estimates of the probability of success for calculations of the relative risk.

Cumulative incidence of methotrexate intolerance within one year: The Kaplan Meier survival analysis estimate of the cumulative incidence of a MISS score of 6 or more points within 52 weeks of study enrollment, as defined above. Kaplan-Meier curves will be constructed separately for intervention and control groups and the curves will be compared using the log-rank test.

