In addition to estimates of intolerance-free survival and cumulative incidence of events, figures will show the corresponding Kaplan Meier curves from enrolment to 52 weeks with a table of subjects at risk in intervention and control groups at 10-week intervals underneath each figure.

13 Reporting Conventions

Medians and 25th, 75th centiles will be reported to one decimal place if applicable. Means and standard deviations for MISS scores and quality of life scores will be rounded to one decimal place. Time will be reported in full weeks throughout. Percentages will be rounded to 1 decimal place. P values will be reported to 3 decimal places. Any p values smaller than 0.001, will be reported as p<0.001. Kaplan Meier estimates of the probability of survival and cumulative incidence of events of interest will be reported as percentages with one decimal place.

14 Quality Assurance of Statistical Programming

The OPT-JIA interim and final statistical analyses will be conducted by the PhD student [name] and the results and statistical code will be verified by [name].

All final statistical code and outputs will be filed in the OPT-JIA files at the BC Children's Hospital network computer servers.

Any outputs will have the

- date and time included
- the name of the code file that produced the analysis
- the author

At the start of any code file there will be a set of comments that give

- the author
- the date and time of writing
- references to inputs and outputs
- reference to any parent code file that runs the child code file

15 Summary of Changes to the Statistics

Changes to the statistical analysis outlined in the OPT-JIA protocol V3, September 2, 2019, concerned primarily the interim analysis (described in the following paragraphs). There were no changes to the 6-monthly safety analyses. The changes of note for the final efficacy analysis were the use of Kaplan Meier estimates to allow for patients with incomplete follow-up and calculate the risk ratio, and the use of a modified per protocol analysis that included participants who stopped medications before 3 months because of intolerance or toxicity.

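### SAP 10.1 counts stopping ondansetron as a primary-endpoint failure, which conflicts with the two-component endpoint in 5.2, 9.2, 10.1 itself and Table 4

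*SAP*

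**What the plan says.** Section 5.2 defines the primary endpoint as "Proportion of subjects that remain on methotrexate with no intolerance one year after starting methotrexate", with intolerance meaning a MISS of 6 or more. Section 9.2 describes intolerance as one of two failure criteria. Section 10.1 opens the same way: "The primary endpoint (remain on methotrexate with no intolerance one year after starting methotrexate) has two components", and names them as staying on methotrexate and having no intolerance.

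Later in 10.1, the relative risk is defined on children who remain on methotrexate with no intolerance. The next sentence adds: "Subjects stopping ondansetron or methotrexate for toxicity or lack of efficacy will be counted as trial failures in calculations for the primary endpoint", irrespective of MISS. The primary row of mock Table 4 is labelled with the two components only.

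Two other places bear on this. The interim rule in 8.5.3 declares failure if any of "the criteria for failure -- stopping methotrexate or experiencing intolerance -- were observed during any visit" up to 52 weeks. Section 7 plans on "expected methotrexate continuation with no intolerance of 50% in the control group and 75% in the intervention group".

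On exposure, 6.3 gives ondansetron routinely to the intervention arm. In the control arm it is "prescribed only to those who develop methotrexate-induced nausea/vomiting during usual care".

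**The concern.** The same child can be scored two ways on the primary endpoint, and no sentence reconciles them. The primary RR then depends on which sentence the programmer follows, in an open-label trial that has already had its interim look.

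The clause reads the same for both arms, but the arms are not equally exposed to it. A child who never receives ondansetron cannot fail by stopping it. The extra failures should therefore gather in the intervention arm, lowering the RR and costing power.

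The clause also has no working definition. For methotrexate, 10.1 supplies a coded variable, an exception for temporary holds and a route for resolving unclear cases. For stopping ondansetron the primary-endpoint text supplies none of these. The source rule in 10.2 covers whether the child is receiving ondansetron, for the per-protocol analysis, and not why it was stopped.

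**Working it through.** **1. One child, each rule.** Take a child who stops ondansetron for toxicity, stays on methotrexate for the year and never records a MISS of 6 or more.

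| Place in SAP | Score |
|---|---|
| 5.2 endpoint | success |
| 9.2 two criteria | success |
| 10.1 opening, two components | success |
| 10.1 definition of the RR | success |
| Table 4 row label | success |
| 8.5.3 interim rule | success |
| 10.1 sentence on stopping ondansetron | failure |

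**2. The plan's own sample size.** Section 7 gives 79 evaluable per group for 50% vs 75%, 90% power and p<0.05 (taken as two-sided). The log-RR formula with a pooled null variance gives 80.0 per group, and power of 0.896 at 79. The unpooled log-RR formula gives 85.2 per group, and power of 0.877 at 79. For dropout, 158/0.90 = 175.6, so 176. The stated figures are reproduced closely enough, and the sample-size arithmetic is not in question.

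**3. Effect of the clause.** The SAP gives no ondansetron stopping rate, so these are assumptions:
- s = share of otherwise successful children exposed to ondansetron who stop it for toxicity or lack of efficacy;
- c = share of otherwise successful controls who received it.

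The formulas (unpooled) are:
- p1 = 0.75(1 − s) and p0 = 0.50(1 − c·s);
- SE = √[(1 − p1)/(79·p1) + (1 − p0)/(79·p0)];
- power = Φ(ln(p1/p0)/SE − 1.96).

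Base case: SE = √[0.25/59.25 + 0.50/39.5] = 0.1299, and ln 1.5 = 0.4055. Power = Φ(0.4055/0.1299 − 1.96) = 0.877.

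Example, s = 5% and c = 0: p1 = 0.7125, RR = 0.7125/0.50 = 1.425, SE = 0.1333, power = 0.757.

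| s | Intervention successes re-scored (59.25·s) | RR, power (c = 0) | RR, power (c = 50%) |
|---|---|---|---|
| 0 | 0 | 1.500, 0.877 | 1.500, 0.877 |
| 1% | 0.6 | 1.485, 0.857 | 1.493, 0.863 |
| 3% | 1.8 | 1.455, 0.811 | 1.477, 0.833 |
| 5% | 3.0 | 1.425, 0.757 | 1.462, 0.799 |
| 10% | 5.9 | 1.350, 0.592 | 1.421, 0.698 |

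The pooled-null version gives the same pattern: 0.896 at base and 0.780 at s = 5%, c = 0. At the final alpha of 0.05 − 0.0045 = 0.0455, the unpooled figures are 0.869 at base and 0.744 at s = 5%, c = 0.

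**4. Direction.** With arm-specific stopping rates s1 (intervention) and s0 (exposed controls), the RR falls as long as c·s0 < s1. If half of the otherwise successful controls were exposed, they would have to stop at twice the intervention rate to cancel the effect. For example, s1 = 3%, s0 = 6% and c = 50% return RR 1.500.

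**The case against.** The best defence is that the sentence in 10.1 is the only one that addresses a child who stops ondansetron, and it does so explicitly in the section that governs the final analysis. A specific rule ordinarily supplements a general one, and counting a treatment stop as failure is a legitimate composite endpoint. This shows that the clause may be intended. It does not remove the conflict. The component list and the RR definition stand in the same section, and 5.2, 9.2 and Table 4 would all need rewording if the composite were meant.

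Several stronger readings might be inferred and are not supported:
- *That 8.5.3 and section 7 directly contradict the clause.* Section 8.5.3 is a declared interim modification, and section 15 carries its Kaplan-Meier methods forward without expressly carrying the failure rule. Section 7 states planning rates. Both are inconsistencies with the clause and no more.
- *That the clause could push the RR below 1.* On the formulas above this needs s above 33% with c = 0, or above 50% with c = 50%.
- *That the power loss is large.* The 10% row has nothing in the document behind it. Many stops for lack of efficacy would already fail on MISS, so the low end is more plausible.
- *That the clause helps the intervention.* The expected bias runs against it and does not inflate false positives.

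The objection to simply deleting the clause also stands. Deletion would come after an open-label interim and in the direction that favours the intervention. Section 15 does not list the clause as new ("The changes of note for the final efficacy analysis were the use of Kaplan Meier estimates to allow for patients with incomplete follow-up", plus the modified per-protocol set), so it may come from the protocol, which is not shown.

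**Conclusion.** The conflict is real and sits in the rule that determines the primary result, so it should be settled before final database lock. Its numerical effect is unknown. With 1–5% of otherwise successful intervention children and no controls re-scored, the RR is 1.49–1.43 against a planned 1.50, and power is about 0.86–0.76 against 0.88 at 79 per group. In children, that is roughly 0.6 to 3 of about 59 expected intervention successes.

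These figures rest on assumed stopping rates, on ondansetron stops being more frequent per otherwise successful child in the intervention arm, and on the planning sample size. Section 8.5.7 has the sample size re-estimated after the interim, so 79 per group is only the planning case. The document alone cannot show which rule the sponsor intended, but five definitions in the plan, as well as the interim rule, point to the two-component one.

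**What to change.** 1. Check the clause against the protocol. If the protocol contains it, log the change below as a post-interim departure.
2. Before final lock, state one failure rule in 10.1: a permanent methotrexate stop for any reason (temporary holds excepted, as 10.1 already provides) or any MISS of 6 or more by 52 weeks. This means deleting the words *ondansetron or*. It also removes the toxicity or lack-of-efficacy qualifier on methotrexate stops, and the SAP should say so, because a permanent stop for another reason, such as inactive disease, then counts as failure.
3. Apply the rule to every child, including those in the interim. This is feasible because "all available registry visits for all OPT-JIA participants will be provided to conduct the final analysis".
4. In either case, report the version that also counts ondansetron stops for toxicity or lack of efficacy as a pre-specified sensitivity analysis. Use the same Kaplan-Meier RR and place it beside the primary result in Table 4.
5. Record in section 15 that the choice was made after the interim, that it matches the interim failure rule, and that its direction favours the intervention.

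The cost is a short text edit, one section 15 entry, one extra analysis and one table row. Ondansetron status is already collected, but reasons for stopping may need site queries. The drawback is that ondansetron toxicity leaves the primary endpoint and appears only in the safety and sensitivity results. For that reason both versions must be shown.

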8.4 Missing Data

(ICH E3; 9.7.1, 11.4.2.2. ICH E9;5.3. EMA Guideline on Missing Data in Confirmatory Clinical Trials)

During ongoing quality control of data entered in the study database, data from a study visit is reviewed by the study registry coordinator within 2 weeks of being entered and queries are sent to the site regarding any missing or apparently spurious data. Once these queries are answered satisfactorily, the data for that visit is locked. Only data contained in locked visits will be used for trial analyses.

In preparation for the interim and final analyses, the study statistician will perform further examination of the data for outlier values. Values outside a plausible range (e.g. an erythrocyte sedimentation rate >200 mm/h) will be converted to missing values.

After receiving the locked study dataset for the final analysis and dealing with values outside a plausible range, missing values will be imputed if needed using multiple imputations by chained equations.

Missing MISS questionnaire scores will not be imputed. Subjects with missing MISS questionnaire scores while still receiving methotrexate will be considered as censored as of the last available visit with a valid MISS score.

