8.5.4 Stopping Rules

As per the study protocol, the Data and Safety Committee assess results of the preliminary analysis according to the following guidance:

- If the CI is entirely below a relative risk of 1.2, the study will be stopped for futility.
- If the CI is entirely above a relative risk of 1.2, the study will be stopped and superiority will be claimed.
- If the CI includes a relative risk of 1.2, the trial will continue until the re-calculated full target sample is attained.

The RR of 1.2 was selected on clinical grounds. In a prospective study of 142 children with JIA starting methotrexate followed for one year, Van Dijkhuizen et al reported that 59 patients developed intolerance and 11 discontinued methotrexate for other reasons, for a total of 72 (50.7%) remaining on methotrexate with no intolerance [18]. An increase in this proportion to <60% is deemed too small to justify the additional costs and risks of adding prophylactic ondansetron.

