16. Bilder CR, Loughin TM (2014) *Analysis of Categorical Data with R.* Boca Raton, FL: Chapman and Hall/CRC Press
18. van Dijkhuizen EH, Bulatović Čalasan M, Pluim SM, de Rotte MC, Vastert SJ, Kamphuis S, de Jonge R, Wulffraat NM. Prediction of methotrexate intolerance in juvenile idiopathic arthritis: a prospective, observational cohort study. *Pediatr Rheumatol Online J.* 2015 Feb 18;13:5.
20. Lawless, J. F. (2003) *Statistical Models and Methods for Lifetime Data.* Hoboken, NJ: John Wiley and Sons.

16 Listing of Tables, Listings and Figures

The 6-monthly Safety reports include:

- A Table 1 comparing baseline characteristics of intervention and control participants.
- A Table 2 listing all observed adverse events.

The Interim Analysis report includes:

- A Table 1 comparing baseline characteristics of intervention and control participants.
- A Table 2 listing efficacy outcomes to date in the intervention group.
- A Table 3 listing efficacy outcomes to date in the control group.
- A Table 4 listing all observed adverse events.
- A Figure 1 showing patient disposition organized as per the CONSORT statement.
- A Figure 2 showing Kaplan Meier survival curves for intolerance free survival for intervention and control groups.

The final Analysis Report includes:

- A Table 1 comparing baseline characteristics of intervention and control participants.
- A Table 2 listing efficacy outcomes in the intervention group.
- A Table 3 listing efficacy outcomes in the control group.
- A Table 4 summarizing efficacy outcomes in intervention and control groups in side-by-side columns, with p values for the comparisons.
- A Table 5 listing all observed adverse events.
- A Table 6 comparing adverse events in intervention and control groups.
- A Figure 1 showing patient disposition organized as per the CONSORT statement.
- A Figure 2 showing Kaplan Meier survival curves for intolerance free survival for intervention and control groups.
- A 4-panel Figure 3 showing cumulative incidence curves for methotrexate intolerance, attainment of inactive disease, starting biologic medications, and experiencing an adverse event.

The manuscript for publication includes:

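### Kaplan-Meier incidence of methotrexate intolerance: children who stop methotrexate for other reasons are left unhandled, and censoring them would overstate the incidence slightly

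*SAP*

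**What the plan says.** Section 10.1 sets the estimator for this secondary endpoint: "The Kaplan Meier survival analysis estimate of the cumulative incidence of a MISS score of 6 or more points within 52 weeks". Curves are drawn separately by arm, and "the curves will be compared using the log-rank test". Section 16 carries the result into a panel of Figure 3, in both the final report and the manuscript.

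The SAP treats stopping methotrexate for other reasons as an event distinct from intolerance in two places:

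- Section 8.5.4 reports of its reference cohort that "59 patients developed intolerance and 11 discontinued methotrexate for other reasons, for a total of 72 (50.7%) remaining on methotrexate with no intolerance".
- Section 10.1 absorbs certain stops into the primary endpoint: "Subjects stopping ondansetron or methotrexate for toxicity or lack of efficacy will be counted as trial failures in calculations for the primary endpoint".

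No matching rule exists for the intolerance endpoint. Section 8.4 has the only censoring rule written for MISS: "Subjects with missing MISS questionnaire scores while still receiving methotrexate will be considered as censored". It does not reach children who have stopped. Section 9.2 derives an ever/never indicator, which is zero for a child with no recorded MISS score of 6 or more, but gives no date at which a child who stopped leaves the risk set. No competing-risk method appears anywhere in the SAP.

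**The concern.** Kaplan-Meier assumes that a censored child would have gone on to fail at the same rate as the children still under observation. That is reasonable for a child whose data are merely missing. It is not reasonable for a child who has permanently come off the drug, because intolerance to that drug is then largely precluded. If such stops are censored, one minus Kaplan-Meier estimates the risk in a hypothetical setting where nobody stops for another reason. It is no longer the share of children who become intolerant, which is what the endpoint's name promises.

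At stake are one reported secondary percentage per arm, its figure panel and the numbers at risk beneath it. Because the SAP leaves the handling open, two analysts following it could publish different incidences from the same data. The trial is open-label, so the choice is better fixed before the final analysis.

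**Working it through.** **Inputs.** From SAP section 8.5.4: 142 children followed for one year, 59 with intolerance, 11 stopped for other reasons. From section 7: planned success of 50% in control and 75% in intervention, and 79 evaluable children per group.

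**Reproducing the SAP's figure.** 142 − 59 − 11 = 72, and 72/142 = 50.7%, as stated. The crude shares are 59/142 = 41.5% intolerant (I) and 11/142 = 7.7% other stops (C).

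**Formula if stops are censored.** With constant, proportional cause-specific hazards and no other censoring, one minus Kaplan-Meier at one year is

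1 − (1 − I − C)^(I/(I + C)).

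The cumulative incidence function is I itself.

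**Cohort (control-like) rates.** 1 − 0.507^(59/70) = 43.6%, against 41.5%: +2.0 points, ratio 1.05.

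**Timing bounds, without constant hazards.**

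- All other stops after the intolerance events: 59/142 = 41.5%, no excess.
- All other stops before them: 59/(142 − 11) = 59/131 = 45.0%, +3.5 points.

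**Planned intervention rate (25% total failure).** The SAP does not split this failure by cause, so two assumptions are shown.

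- Other stops keep the cohort's 11/70 share of failures: I = 0.25 × 59/70 = 21.1%; 1 − 0.75^(59/70) = 21.5%; +0.5 point.
- Other stops stay at 7.7%: I = 25% − 7.7% = 17.3%; 1 − 0.75^(0.1725/0.25) = 18.0%; +0.8 point.

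**If stops are kept at risk to week 52 as non-events.** One minus Kaplan-Meier equals the crude incidence, so the excess is zero. A simulation of 200,000 children per scenario agrees:

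| Scenario | True incidence | Stops censored | Stops kept as non-events |
|---|---|---|---|
| Cohort rates | 41.7% | 43.7% | 41.7% |
| Intervention, 11/70 share | 21.1% | 21.5% | 21.1% |
| Intervention, 7.7% other stops | 17.3% | 18.1% | 17.3% |

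**Sensitivity to an assumed stop rate.** The SAP gives no rate of other stops for this trial. Holding intolerance at 41.5%, assumed rates of 5%, 10%, 15% and 20% give excesses of +1.3, +2.7, +4.2 and +6.0 points. The two highest rates imply total failure of 56.5% and 61.5%, beyond the planned 50% in control. With total failure held at 50% and 15% other stops, intolerance is 35% and the formula gives 1 − 0.5^(0.35/0.50) = 38.4%, +3.4 points.

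**Coherence.** At cohort rates with stops censored, 50.7% success plus 43.6% intolerance leaves 5.7% for other stops, when 7.7% stopped. Aalen-Johansen components add up to the whole.

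**The case against.** The strongest reply is that the SAP nowhere says these children are censored, and several provisions lean the other way. The section 8.4 rule is confined to children still on methotrexate. The section 9.2 indicator gives zero to a child who stops without a high score. MISS is scheduled at every visit (section 6.4), all registry visits go into the final analysis (section 10.1), and section 10 keeps every randomized child. The general convention in section 8.5.3, written for the primary endpoint, censors at the last visit rather than at stopping the drug. A reader might infer from the words Kaplan-Meier that the published incidence will certainly be too high. The documents do not support that, and this part of the reply stands in full. What it leaves untouched is that the handling is unspecified.

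Second, the effect is small beside sampling error. With 79 children, the 95% half-width around 41.5% is 1.96 × √(0.415 × 0.585/79), about 11 points. This also stands. A larger bias can be produced only with stop rates that the SAP does not contain.

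Third, the risk of intolerance in the absence of other stopping is a recognised target for a tolerability question. That is fair, but it would have to be declared and would not be called cumulative incidence.

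Finally, no trial decision turns on this endpoint, and if stops are censored the log-rank test remains a valid comparison of cause-specific hazards. Both points are correct.

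**Conclusion.** The concern holds as a minor one. The SAP names an estimator of cumulative incidence that does not treat other-reason stopping as a competing event, and it omits the rule that would decide whether this matters. The direction is conditional: upward if stops are censored at stopping, none if they are kept at risk to week 52. In the first case the size is about 2 points at the cited cohort's rates and 0.5 to 0.8 point at the planned intervention rate. These figures rest on constant hazards, on the cohort's rates applying to this trial, and on an assumed split of failures in the intervention arm. Higher stop rates would enlarge the bias but are assumptions.

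A reader might also infer that the primary result is affected. It is not, because stopping methotrexate already counts as failure there (sections 8.5.3 and 10.1).

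**What to change.** In section 10.1, replace Kaplan-Meier for this endpoint with the Aalen-Johansen cumulative incidence function by arm. The event is a first MISS score of 6 or more. The competing event is permanent methotrexate stopping without a prior score of 6 or more, with temporary holds treated as section 10.1 already treats them. State that censoring is reserved for withdrawal, loss to follow-up or missing MISS. Either keep the log-rank test and label it a cause-specific comparison, or use Gray's test if the incidences themselves are to be compared. Change the matching Figure 3 panel in section 16 to the same estimate.

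The cost is a sentence or two and a standard routine. No new data are needed, since methotrexate status is recorded at every visit. The reported incidences would be slightly lower than if these stops were censored.
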